9.13.4 Health Economic Outcomes

9.13.4.1 EuroQol-5 Dimensions-5 Levels and EuroQol Visual Analog Scale

The combination of 5 scores for EQ-5D-5L and the VAS will be presented as:

Changes in the index value from baseline to each time point

Change in the VAS score from baseline to each time point

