### **3.6 Health Economic Outcomes Research Objective**

- To compare the total quality-of-life change by measuring the EuroQol-5 Dimensions-5 Levels (EQ-5D-5L) and a work productivity (WP) questionnaire in patients treated with S-033188 compared with oseltamivir 75 mg BID for 5 days and placebo

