## 9. EFFICACY ANALYSIS

In the ITTI Population that is the primary analysis population, the primary endpoint and all secondary endpoints will be analyzed. For the PPS that is a secondary analysis population, only the primary endpoint will be analyzed. Table 3 summarizes the primary

endpoint, secondary endpoints, other endpoints and statistical methods used to analyze these endpoints. The detailed statistical methods are described in later sections.

The analysis of each efficacy endpoint will consist of comparison between the S-033188 group (40 mg and 80 mg combined) and the placebo group using data of the two age strata pooled (i.e., 12 to 64 years age), and comparison between the S-033188 group (40 mg and 80 mg combined) and the oseltamivir group using data of 20 to 64 years age stratum.

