**Table 3 Statistical Methods Used to Analyze Each Endpoint**

	Endpoint Analysis	Statistical Method
Primary Endpoint	Time to alleviation of symptoms	1, 2, 9, 10, 11
Secondary Endpoints	Proportion of patients positive for influenza virus titer	3, 13
	Proportion of patients positive by RT-PCR	3, 13
	Change from baseline in virus titer	4, 12
	Change from baseline in the amount of virus RNA (RT-PCR)	4, 12
	Area under the curve adjusted by baseline in virus titer	4, 12
	Area under the curve adjusted by baseline in the amount of virus RNA (RT-PCR)	4, 12
	Time to cessation of viral shedding by virus titer	1, 9, 10,11
	Time to cessation of viral shedding by RT-PCR	1, 9, 10,11
	Proportion of patients whose symptoms has been alleviated	3, 13
	Time to alleviation of the 4 systemic symptoms	1, 9, 10,11*
	Time to alleviation of the 3 respiratory symptoms	1, 9, 10,11*
	Change from baseline in composite symptom score	6, 12
	Time to resolution of fever	1, 9, 10,11
	Proportion of patients reporting normal temperature	3, 13
	Body temperature	6, 12
Time to alleviation of individual symptoms	1, 9, 10,11*	
Time to return to preinfluenza health status	1, 9, 10,11*	
Incidence of influenza-related complications	5, 13	
Other Endpoints	Serum influenza antibody titer	7, 13, 14
	Polymorphic and treatment-emergent amino acid substitutions in the PA gene of evaluable virus	13
	Drug susceptibility in patients with evaluable virus	12
	EQ-5D-5L and EQ VAS	12
	Work productivity questionnaire	12
	Intrahousehold infection rate	8

\* Treatment group difference in median time

[Statistical test methods]

1. Stratified Peto-Prentice's generalized Wilcoxon test

2. Stratified log rank test
3. Mantel-Haenszel test
4. van Elteren test
5. Fisher's exact test
6. Analysis of covariance (ANCOVA)
7. Wilcoxon rank sum test
8. Poisson regression model  
    [Summarization methods]
9. Kaplan-Meier curve
10. Median time and its 95% CI
11. Treatment group difference in median time and its 95% CI (Bootstrap method)
12. Summary statistics (continuous variables)
13. Summary statistics (categorical variables)
14. Geometric mean

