#### 4) EQ-5D-5L and EQ VAS

These endpoints consist of the change from baseline in the index value calculated from the EQ-5D-5L questionnaire and that in EQ VAS score on Day 1, 2, 3, 4, 5, 6, 7, 8, 9, 10, 11, 12, 13, 14 and 22. The index value will be recorded twice daily (morning and evening) from Day 1 to Day 9, and once daily (evening) from Day 10 to 14, and Day 22. A conversion table proposed by Ikeda et al. (2015) [1] will be used to convert EQ-5D-5L status to index value.

The EQ-5D-5L and EQ VAS data obtained when e-diary is set up after initial administration will not be used for analysis. Because these data may be observed due to e-dairy system's incorrect setting. In addition, the EQ-5D-5L and EQ VAS data observed in the evening after Day 15 will be excluded from this analysis. Because these data may be observed at unplanned time point in the protocol due to e-dairy system's incorrect setting. Only if evening data observed on the last visit date but no data whose timepoint is 'Visit' are collected, the data will be included in the analysis.

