- The summary statistics for change in the index value and change in VAS score will be presented by treatment group at each scheduled time point.

5) Work Productivity Questionnaire

- The summary statistics for the percentage of absenteeism due to influenza illness and the percentage of work productivity loss due to influenza illness will be presented by treatment group.
- For Question 4 in Work Productivity (WP) Questionnaire, the summary statistics for the number of days required for personal assistance will be presented by treatment group. One day is equal to 24-hours.

6) Intrahousehold infection rate

Let  $K$  be the total number of patients included in this analysis,  $y_k$  be the number of  $k^{\text{th}}$  patient's household members infected between Day 1 and Day 15, and  $n_k$  be the number of  $k^{\text{th}}$  patient's household members uninfected by Day 1 ( $k = 1, \dots, K$ ). Under the assumption that  $y_k$  is distributed according to Poisson distribution with mean  $\mu_k$ , the following Poisson regression model will be applied;

$$\log(\mu_k) = \log(n_k) + \beta_0 + \beta_1 x_k$$

In the model,  $x_k$  is a group indicator variable for the  $k^{\text{th}}$  patient, i.e.,  $x_k = 1$  for the S-033188 group,  $x_k = 0$  for the control group (the placebo group or the oseltamivir group). The  $\beta_0$  is an intercept parameter,  $\beta_1$  is a regression parameter. Intrahousehold infection rates for the S-033188 group and the control group are given by  $\exp(\beta_0 + \beta_1)$  and  $\exp(\beta_0)$ , respectively. Estimate and 95% CI of intrahousehold infection rate of each treatment group and comparison between two treatment groups will be carried out using the following SAS code. In addition, a risk ratio of the S-033188 group to the control group and the corresponding 95% CI will be estimated by the above Poisson regression model.

```
Data analysisdata;  
  set analysisdata;  
  lnum=log(NUM);  
run;
```

[Comparison between the S-033188 group and the placebo group]

```
proc genmod data = analysisdata;  
  class TRTP;  
  model RES = TRTP / dist = poisson link = log offset = lnum;  
  lsmeans TRTP / cl exp;  
  estimate "S-033188 vs Placebo" TRTP 1 -1 / exp;  
run;
```

- NUM: Number of household members uninfected by Day 1
- TRTP: Treatment group (1:S-033188, 2:Placebo)
- RES: Number of household members infected between Day 1 and Day 15

[Comparison between the S-033188 group and the Oseltamivir group]

```

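### The objective is to compare total quality-of-life change, but for EQ-5D-5L both documents plan only arm summaries at each time point, with no measure over the illness and no between-arm estimate

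*SAP*

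**What the plan says.** **Objective.** SAP 3.6 reads "To compare the total quality-of-life change by measuring the" EQ-5D-5L and a WP questionnaire, for S-033188 against oseltamivir and placebo. Protocol 2.6 sets the same aim.

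**EQ-5D endpoint.** SAP 9.3, item 4: "These endpoints consist of the change from baseline in the index value calculated from the EQ-5D-5L questionnaire and that in EQ VAS score", listed by day. On timing: "The index value will be recorded twice daily (morning and evening) from Day 1 to Day 9, and once daily (evening) from Day 10" to Day 14, with a last record on Day 22.

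**EQ-5D analysis.** SAP 9.5, item 4: "summary statistics for change in the index value and change in VAS score will be presented by treatment group". SAP Table 3 gives EQ-5D-5L and EQ VAS a single method code, 12, which is summary statistics for continuous variables. Protocol 9.13.4.1 lists "Changes in the index value from baseline to each time point" and the matching change in VAS, and nothing more.

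**WP.** SAP 9.3, item 5 derives two percentages per patient over a 21-day denominator: absenteeism and work productivity loss. SAP 9.5, item 5 then plans "summary statistics for the percentage of absenteeism due to influenza illness and the percentage of work productivity loss due to influenza illness" by arm. Table 3 again shows code 12 only.

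**The concern.** An objective to compare a total change needs two things from the analysis: a quantity that covers the period of interest, and an estimate of how the arms differ on it. For EQ-5D-5L the plan specifies neither.

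EQ-5D is recorded up to twice daily through Day 9 and daily to Day 14, a schedule dense enough to support a measure over the illness. A reader of the planned tables would see a long series of arm means and would have to judge the overall picture informally. Any integrated measure or formal contrast produced later would be post hoc, with the time span, baseline and method chosen after unblinding.

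**Working it through.** No power, alpha or sample-size figure is at issue, so the check is a count and a comparison of sections.

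**1. Number of summaries planned.** Inputs are from SAP 9.3, item 4.
- Days 1 to 9, twice daily: 9 × 2 = 18
- Days 10 to 14, once daily: 5 × 1 = 5
- Day 22: 1
- Total: 18 + 5 + 1 = 24 scheduled occasions

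Cross-check with the diary windows in SAP Table 2-1:
- 12 to 216 hours in steps of 12: (216 − 12)/12 + 1 = 18
- 240 to 336 hours in steps of 24: (336 − 240)/24 + 1 = 5
- 528 hours: 1
- Total: 24, in agreement

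The count is an upper limit, because Day 1 entries depend on when dosing starts (Protocol 7.4.1). With two measures, index and VAS, there are up to 2 × 24 = 48 summaries per arm.

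**2. Totals and contrasts planned for EQ-5D.** In Protocol 9.13.4.1, SAP 9.3, SAP 9.5 and SAP Table 3 there is no AUC, sum or time-average, and no between-arm difference, confidence interval or test. Both counts are zero.

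**3. Is this a general rule for the SAP's other endpoints?** Table 3 lists six. Two carry a test code: serum antibody titer (code 7, Wilcoxon rank sum) and intrahousehold infection rate (code 8, Poisson regression, with a risk ratio and 95% CI in SAP 9.5). Four do not: PA substitutions, drug susceptibility, EQ-5D and WP. So endpoints in this class can receive a comparison.

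**4. Does the SAP already hold the tools?** Yes.
- SAP 9.2, item 5 gives a trapezoidal AUC of change from baseline for virus titer: Σ (y_k + y_{k−1} − 2y_0)(t_k − t_{k−1})/2.
- SAP 9.4, item 7 gives an ANCOVA that reports a difference in least-squares means, its SE and 95% CI. Item 10 adds the outcome's own baseline as a covariate for body temperature.

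**5. Could a reader rebuild the comparison from the planned tables?** Only in part. SAP 6.1 summaries include n, mean and SD, so an unadjusted difference and interval can be computed at one time point. If the same patients contribute throughout, the arm mean of an AUC is a weighted sum of the time-point means. Its standard error, however, depends on the within-patient correlations between time points, which the tables do not show.

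**6. Who would be in the tables.** SAP 9.5 names no analysis population or age set for EQ-5D. Planned ITTI numbers (Protocol 9.2) for S-033188 are 62 aged 12 to 19 and 350 aged 20 to 64, so adolescents are 62/412 = 15.0% of that arm. The oseltamivir arm has none. Unless the age rule in SAP 9 is taken to cover EQ-5D, the table would set ages 12 to 64 beside ages 20 to 64.

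**The case against.** **The objective is wider than EQ-5D.** A reader might infer that the whole objective lacks a total. The documents do not support that: the objective also names WP, and both WP percentages accumulate over 21 days. This stands, and limits the missing total to EQ-5D. WP still has no between-arm estimate.

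**The SAP follows the Protocol.** A reader might also infer an undeclared departure by the SAP. There is none: Protocol 9.13.4.1 is equally descriptive, so SAP 14 had nothing to declare. The mismatch is between objective and analysis in both documents.

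**A general comparison rule exists.** SAP 9 states: "The analysis of each efficacy endpoint will consist of comparison between the S-033188 group (40 mg and 80 mg combined) and the placebo group", and likewise for oseltamivir in ages 20 to 64. But it speaks of efficacy endpoints, EQ-5D is listed among the other endpoints, and neither Table 3 nor SAP 9.5 gives it a method of comparison.

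**The word total may mean across dimensions.** Neither document defines it, and the index does combine five dimensions. This is a possible reading. Even so, an index change at one time is not a total change over an illness, and the reading leaves the comparison missing.

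**Comparing need not mean inference.** The safety objectives use the same verb, while laboratory values, vital signs and ECG are only summarised. That is fair, but SAP 10.1 does test adverse event proportions with Fisher's exact test, so the safety objective gets some formal comparison.

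**Quality of life is tested elsewhere.** Protocol 7.9.5 links time to return to preinfluenza health status to quality of life, and the SAP tests it. It comes from a separate 0 to 10 health scale (Protocol 7.4.1.3), so it does not serve an EQ-5D objective.

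**Conclusion.** The concern holds in this form: for EQ-5D-5L index and VAS, both documents set an aim of comparing total change and then plan only arm summaries at up to 24 time points (up to 48 summaries per arm over the two measures), with no measure over the illness and no between-arm difference or interval. The WP half has 21-day totals but no between-arm estimate.

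The point is minor. The hierarchy covers only the two comparisons of the primary endpoint, so type I error control, power and the primary conclusion are unaffected. The conclusion rests on reading total as a change over the illness; on the narrower reading, only the missing comparison remains.

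**What to change.** In SAP 9.3 and 9.5, add for each patient a trapezoidal AUC of change from baseline in EQ-5D index and in VAS, Day 1 to Day 14, using the virus titer formula. Three details must be set in advance:
- **Baseline.** Use the Day 1 predose value defined in SAP 6.5.2. Protocol 7.7.4.1 describes the Day 22 record as a way to estimate baseline quality of life. That value is post-treatment, so the SAP should say which is used.
- **Missing entries.** SAP 6.4 does not impute, so apply the trapezoid over the available diary entries and state a minimum-data rule. The virus titer AUC has a precedent in requiring an available Day 9 sample.
- **Population.** Name the analysis population, and use ages 12 to 64 against placebo and ages 20 to 64 in both arms against oseltamivir.

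Compare arms by ANCOVA adjusted for the baseline EQ-5D value, baseline composite symptom score and region, reporting the difference and 95% CI. ANCOVA is preferable to the van Elteren test here because the latter, as the SAP uses it, yields only a p value. Report a difference and interval for the two WP percentages in the same way, without the outcome-baseline term since WP has none. Label all of this exploratory and outside the type I error hierarchy.

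The cost is a small amount of programming on data already planned for collection, and a few more exploratory estimates to interpret. If the sponsor does not want them, the lesser remedy is to reword the objective in both documents as descriptive, which removes the mismatch but leaves the question unanswered.

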5.4 Method of Assigning Patients to Treatment Groups

This study will be primarily conducted in Japan, but other Asian countries and the US are also expected to participate. Because of the recommendation in Japan not to use oseltamivir in patients aged < 20 years due to previously reported neuropsychiatric AEs and suicidality in Japan, assignment of patients to treatment groups will be proceeded in each of two age strata, ie, 12 to 19 years age stratum and 20 to 64 years age stratum, separately. Approximately 15% of the whole population to be enrolled in this study will

be patients in 12 to 19 years age stratum.

Patients in 20 to 64 years age stratum will be randomized on a 2:2:1 basis to S-033188 group, oseltamivir group, or placebo group. Patients in 12 to 19 years age stratum will be randomized on a 2:1 basis to either S-033188 group or placebo group. An interactive response technology (IRT) will be used to assign patients to numbers for which treatment has already been randomly assigned. The randomization will also be stratified by region (Japan/Asia, Rest of the world), patients weight (< 80 kg, ≥ 80 kg) and baseline composite symptom score (≤ 11, ≥ 12).

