9.13.5 Intrahousehold infection rate

The definition of the endpoint and the analysis method for the endpoint will be specified in the SAP.

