proc genmod data = analysisdata;  
  class TRTP;  
  model RES = TRTP / dist = poisson link = log offset = lnum;  
  lsmeans TRTP / cl exp;  
  estimate "S-033188 vs Oseltamivir" TRTP 1 -1 / exp;  
run;
```

- NUM: Number of household members uninfected by Day 1
- TRTP: Treatment group (1:S-033188, 3:Oseltamivir)
- RES: Number of household members infected between Day 1 and Day 15

The similar Poisson regression model will be applied using the number of household members  $y_k$  infected during each of the following time periods as a response variable;

- From Day1 to Day 3
- From Day 1 to Day 4
- From Day1 to Day 6
- From Day 1 to Day 11

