## 9.6 Subgroup Analyses for Primary and Secondary Endpoint

Analyses of time to alleviation of symptoms (Section 9.1.1.1, 9.1.1.2, Kaplan-Meier curve, the median time to alleviation of symptoms and its 95% CI) will be presented for the following subgroup 1), 2), 3) and 4).

Subgroup analyses will be performed for the ITTI Population in the following subgroups.

1) Total score of influenza symptoms at baseline

- $\leq 11$  points
- $\geq 12$  points

Stratified Peto-Prentice's generalized Wilcoxon test with region (Japan/Asia or Rest of the world) as stratification factors will be applied.

2) Region

- Japan/Asia
- Rest of the world

Stratified Peto-Prentice's generalized Wilcoxon test with composite symptoms score at baseline ( $\leq 11$  or  $\geq 12$ ) as stratification factors will be applied.

3) Body weight

- $< 80$  kg
- $\geq 80$  kg

4) Influenza virus type based on RT-PCR

- A/H1pdm
- A/H3
- B

5) Time to treatment from flu onset

- 0 hours  $\leq$  to  $\leq 24$  hours
- 24 hours  $<$  to  $\leq 48$  hours

Analyses of time to alleviation of symptoms (Section 9.1.1.1, 9.1.1.2, the median time to alleviation of symptoms and its 95% CI) will be presented for the following subgroup 5) and 6).

6) Meals before and after dosing

- Dosing > 4 hours before or > 4 hours after food taken
- Dosing within 2-4 hours before or 2-4 hours after food intaken
- Dosing < 2 hours before or < 2 after food intaken

If a subject has had meals both before and after dosing, the priority will be given to a category closer to the time of dosing. If multiple applicable categories exist even under this condition, data obtained before dosing will be adopted.

7) Age

- < 18 years
- ≥ 18 years

For the proportion of patients positive for influenza virus titer/RT-PCR, change from baseline in virus titer/amount of virus RNA (RT-PCR), area under the curve adjusted by baseline in virus titer/RT-PCR and time to cessation of viral shedding by virus titer/RT-PCR, these analyses will be presented for the following subgroup 8). Analyses of intrahouse infection rate will be presented for the following subgroup 8)

8) Influenza virus type and subtype based on RT-PCR

- A/H1pdm
- A/H3
- B

For the proportion of patients positive for influenza virus titer, change from baseline in virus titer for the following subgroup 9).

9) Influenza virus type and subtype based on RT-PCR

- A/H1pdm
- A/H3
- B

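### The plain Poisson variance behind the intrahousehold infection rate does not assure nominal size or coverage, in either direction; a household-clustered robust variance is a cheap, minor correction

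*SAP*

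**What the plan says.** SAP 9.5 item 6 uses one row per index patient. The response is "RES: Number of household members infected between Day 1 and Day 15", and the offset is the log of the number of household members still uninfected by Day 1. The SAP assumes that the count "is distributed according to Poisson distribution with mean" μ_k and fits "model RES = TRTP / dist = poisson link = log offset = lnum" in PROC GENMOD, once against placebo and once against oseltamivir. Each arm's rate with its 95% CI, the between-group comparison, and the risk ratio with its 95% CI all come from this fit. Neither code block contains a REPEATED statement, a scale option or a dispersion check.

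Table 3 names a single method for this endpoint, "8. Poisson regression model". Four shorter windows (Day 1 to Day 3, 4, 6 and 11) reuse it: "The similar Poisson regression model will be applied using the number of household members" infected in each period. SAP 9.6 adds virus type: "Analyses of intrahouse infection rate will be presented for the following subgroup 8". SAP section 14 records no relevant change. Protocol 9.13.5 leaves the matter to the SAP: "The definition of the endpoint and the analysis method for the endpoint will be specified in the SAP".

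No document gives an infection risk, a household-size distribution, a within-household correlation or a Japanese sample size. On the last, Protocol 5.4 says only: "This study will be primarily conducted in Japan, but other Asian countries and the US are also expected to participate".

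**The concern.** A Poisson variance equals its mean. Here that fails for two reasons visible in the SAP's own definitions. The count is capped by the number of contacts at risk, so it behaves more like a binomial, with smaller variance. And contacts in one home share an index case and an environment, so their infections are likely to be correlated, which gives larger variance. The two effects cancel only by coincidence.

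What is at stake is the width of the intervals and the meaning of the p values, not the estimated rates or ratios. Protocol 7.9.2 says the endpoint is meant to inform transmissibility after treatment. The model feeds ten full-sample comparisons (five windows × two controls) and is repeated in three virus types.

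**Working it through.** **Inputs from the documents.** Two-sided 0.05 level (SAP 6.2). Planned ITTI of 350 + 62 = 412 on S-033188, 175 + 31 = 206 on placebo and 350 on oseltamivir (SAP 4.3).

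**Assumed inputs.** 1 to 4 contacts per household in equal shares; infection risk p of 5–30%; ICC 0–0.3; one enrolled patient per household; 270 v 135 usable patients (270/412 = 135/206 ≈ 66%), or 230 v 230 against oseltamivir.

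**Step 1: the plan's own figure.** If the counts really are Poisson, the ratio of true to planned variance is φ = 1, and the Wald test has size 2[1 − Φ(1.96/√1)] = 5.0%. Simulation with true Poisson counts gave 3.6–5.3%, with the low values where the smaller arm had about 9–16 events.

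**Step 2: the variance ratio.** With bounded, correlated counts, φ = (1−p)[1 + m·ICC], where m = Σn(n−1)/Σn is the size-weighted n−1. For n = 1, 2, 3, 4 in equal shares, m = (0+2+6+12)/(1+2+3+4) = 20/10 = 2.

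**Step 3: true size, 2[1 − Φ(1.96/√φ)].** Two examples. At p = 0.30 and ICC 0, φ = 0.70 and the size is 1.9%. At p = 0.05 and ICC 0.3, φ = 0.95 × 1.6 = 1.52 and the size is 11.2%. The table gives formula / simulated size (beta-binomial, 20,000 replicates, 270 v 135):

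| Risk | ICC 0 | ICC 0.1 | ICC 0.2 | ICC 0.3 |
|---|---|---|---|---|
| 5% | 4.4 / 3.9% | 6.6 / 6.0% | 8.9 / 8.1% | 11.2 / 10.9% |
| 10% | 3.9 / 3.5% | 5.9 / 5.8% | 8.1 / 7.7% | 10.2 / 10.0% |
| 20% | 2.8 / 2.7% | 4.5 / 4.5% | 6.4 / 6.1% | 8.3 / 8.3% |
| 30% | 1.9 / 1.8% | 3.2 / 3.2% | 4.8 / 4.7% | 6.4 / 6.2% |

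At 230 v 230 the simulated range is 2.1–10.5%.

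**Step 4: break-even.** Setting φ = 1 gives ICC = p/[(1−p)m]. With m = 2 this is 0.026, 0.056, 0.125 and 0.214 at risks of 5, 10, 20 and 30%. With m = 1 the values double (0.053 to 0.429); with m = 3 they fall to 0.018 to 0.143. Below break-even the intervals are too wide, above it too narrow.

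**Step 5: coverage of the 95% CI** at a true risk ratio of 0.67 and ICC 0 / 0.1 / 0.2 / 0.3. Control risk 10%: 96.2 / 94.0 / 91.8 / 89.4%. Control risk 30%: 97.6 / 96.3 / 94.5 / 92.9%.

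**Step 6: household-robust variance,** Σ(y_k − n_k·rate)²/Y² per arm, where Y is the arm's total of infected contacts. Across the settings of Step 3 its size is 4.5–5.4%; coverage in Step 5 is 94.6–95.2%. With 412 v 206 and 140 v 70 the planned size is 1.8–10.0% and the robust size 4.6–5.5%, so the 66% share hardly matters. A second calculation with 1 to 5 contacts (mean 2.3) gave the same pattern.

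**Step 7: where the robust variance does not help.** With 40 v 20 at 3% risk, planned size is 0.5–1.8% and robust size 0.7–1.1%; 26–39% of replicates have an arm with no events and hence no estimable ratio.

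**The case against.** The strongest reply is that the error is small where it is most plausible. At ICC 0.1 and risk 5–20% the planned size is 4.5–6.0%. Sizes of 10% or more need an ICC of 0.3 with risk of 10% or less, and nothing in the documents supports those values. At low ICC the test is merely conservative. The endpoint has no multiplicity control, so its p values are descriptive. All of this stands, and it limits the weight of the point. It does not make the stated intervals right.

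A second reply is that the direction will show in the data: PROC GENMOD prints the Pearson chi-square over its degrees of freedom (simulated median 0.70 at risk 30%, ICC 0; 1.37 at risk 5%, ICC 0.3). That is true, but the SAP plans neither to report it nor to act on it.

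Three stronger readings are tempting, and the documents support none of them.

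- A reader might infer that the planned test inflates false positives. The sign depends on risk and clustering, neither of which is given.
- A reader might infer that a robust variance guarantees nominal behaviour. It is a large-sample result, checked here under one assumed mechanism with one patient per household.
- A reader might infer that patients from the same household were enrolled. Protocol 4.3 does not bar it, but silence is not evidence. In an assumed case (risk 15%, ICC 0.2, 30% of households with two patients) all in the same arm, sizes were 13.8% plain, 11.5% clustered on patient and 6.1% on household. With independent randomisation they were 6.2, 4.4 and 4.6%. Co-enrolment would also raise the question of whether each patient counts as the other's contact, which no variance estimator settles.

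**Conclusion.** The point holds as a minor correction. The planned variance is too large by about 1/(1−p) on one account and too small by about 1+(n−1)ICC on the other, so neither nominal size nor nominal coverage is assured. Under the assumed inputs the true size of the 5% test is about 2–11%. The figures rest wholly on assumed household sizes, risks, ICCs and a Japanese share; the two opposing effects follow from the SAP's definitions, given some within-household clustering.

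A reader might infer that the trial's efficacy conclusions are affected. They are not. SAP Table 3 classes the endpoint as Other (the protocol synopsis lists it as secondary), it is collected in Japan only, and the hierarchy in SAP 6.2 covers only the primary endpoint.

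**What to change.** Keep the Poisson log-link model with offset, so that rates and risk ratios do not change. Put a household identifier in CLASS and add `repeated subject = <identifier> / type = ind` to each PROC GENMOD call, for all five windows, both controls and the virus-type subgroups. Patient ID serves as the cluster when each household has one enrolled patient; the SAP should say so, and say how any other household would be identified and its members counted.

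Do not drop comparisons because an arm has few infected contacts, even at a threshold fixed in advance, because that selects on outcome. In a check of an under-10 rule at ICC 0.1, with true risks of 4% v 10%, 58% of comparisons were hidden, including 78% of the significant ones, and the median risk ratio among those kept was 0.53 against a true 0.40. With no effect and 90 v 45 patients, the kept median was 0.87. Robust coverage in those cells was already about 95% without the rule. Instead, report every pre-specified comparison with its event counts, flag those with few events as unreliable under a large-sample variance, and state the ratio as not estimable when an arm has no events.

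The cost is one statement per model, with the identifier in CLASS, and a few sentences in the SAP. No new data are needed if each household has one enrolled patient. Log-scale intervals would range from about 17% narrower (risk 30%, ICC 0) to 22% wider (risk 5%, ICC 0.3). At risk ratio 0.67, control risk 10% and 270 v 135, the rejection rate moves from 42–44% as planned to 45, 40, 35 and 32% at ICC 0, 0.1, 0.2 and 0.3. Very sparse cells are not rescued.
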